4.3 Withdrawal of patients from study treatment and/or study

Stopping Rules:

Patients must discontinue study treatment if they experience any of the following:

- Pregnancy
- Radiographic and/or symptomatic deterioration attributed to disease progression disease as determined by the investigator
- Intolerable toxicity related to sirolimus and/or durvalumab, including development of an irAE determined by the investigator to be unacceptable given the individual patient's potential response to therapy and severity of the event
- Any medical condition that the investigator or Sponsor determines may jeopardize the patient's safety if he or she continues on study treatment
- Use of another non-protocol-specified anti-cancer therapy

The primary reason for study treatment discontinuation should be documented on the appropriate CRF.

Additional reasons for patient discontinuation include:

- Any medical condition that the investigator or Sponsor determines may jeopardize the patient's safety if he or she continues in the study
- Investigator or Sponsor determines it is in the best interest of the patient
- Patient non-compliance

The Sponsor has the right to terminate this study at any time. Reasons for terminating the study may include, but are not limited to, the following:

Clinical Study Protocol

Investigational Drug Substance: MEDI4736 Sirolimus (Rapamune)

Study Number **19-20015**

Edition Number: 4

Date: **11 February 2022**

- The incidence or severity of adverse events in this or other studies indicates a potential health hazard to patients.
- Patient enrollment is unsatisfactory.

Permanent discontinuation of study treatment

Discontinuation of study treatment, for any reason, does not impact the patient's participation in the study. A patient who decides to discontinue durvalumab or sirolimus will always be asked about the reason(s) for discontinuation and the presence of any AE. The patient should continue attending subsequent study visits, and data collection should continue according to the study protocol. If the patient does not agree to continue in-person study visits, a modified follow-up must be arranged to ensure the collection of endpoints and safety information. This follow-up could be a telephone contact with the patient, a contact with a relative or treating physician, or information from medical records. The approach taken should be recorded in the medical records. A patient that agrees to modified follow-up is not considered to have withdrawn consent or to have withdrawn from the study.

Patients who are permanently discontinued from further receipt of IP, regardless of the reason, will be identified as having permanently discontinued treatment. Patients who are permanently discontinued will enter follow-up (see the SoAs).

All patients will be followed for survival until the end of the study.

Patients who decline to return to the site for evaluations should be contacted by telephone as indicated in the SoAs as an alternative.

Patients who have permanently discontinued from further receipt of IP will need to be discontinued from the IVRS/IWRS.

Lost to follow-up

Patients will be considered lost to follow-up only if no contact has been established by the time the study is completed, such that there is insufficient information to determine the patient's status at that time. Patients who refuse to continue participation in the study, including telephone contact, should be documented as "withdrawal of consent" rather than "lost to follow-up." Investigators should document attempts to re-establish contact with missing patients throughout the study period. If contact with a missing patient is re-established, the patient should not be considered lost to follow-up and evaluations should resume according to the protocol.

Clinical Study Protocol

Investigational Drug Substance: MEDI4736 Sirolimus (Rapamune)

Study Number **19-20015**

Edition Number: 4

Date: **11 February 2022**

In order to support key end points of PFS and OS analyses, the survival status of all patients in the full analysis and the safety analysis sets should be re-checked, this includes those patients who withdrew consent or are classified as “lost to follow up.”

- Lost to Follow up – site personnel should check hospital records, the patients’ current physician, and a publicly available death registry (if available) to obtain a current survival status. (The applicable CRF modules will be updated.)
- In the event that the patient has actively withdrawn consent to the processing of their personal data, the survival status of the patient can be obtained by site personnel from publicly available death registries (if available) where it is possible to do so under applicable local laws to obtain a current survival status. (The applicable CRF modules will be updated.)

Withdrawal of consent

Patients are free to withdraw from the study at any time (IP and assessments) without prejudice to further treatment.

Patients who withdraw consent for further participation in the study will not receive any further IP or further study observation, with the exception of follow-up for survival, which will continue until the end of the study unless the patient has expressly withdrawn their consent to survival follow-up. Note that the patient may be offered additional tests or tapering of treatment to withdraw safely.

A patient who withdraws consent will always be asked about the reason(s) for withdrawal and the presence of any AE. The Investigator will follow up AEs outside of the clinical study.

If a patient withdraws consent, they will be specifically asked if they are withdrawing consent to:

- All further participation in the study including any further follow up (eg, survival contact telephone calls)
- Withdrawal to the use of any samples

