Other adverse events (toxicity) will be listed and summarized overall and by dose level. Adverse events will also be listed by severity, seriousness, and by system organ class. The number and percentage of subjects who experience AEs will be presented in tabular and/or graphical format and summarized descriptively, where appropriate. No formal statistical comparison between the dose levels or PD-L1 will be performed. AEs will be presented with and without regard to causality based on the investigator's judgment. The frequency of overall toxicity, categorized by toxicity grades 1 through 5, will be described. Additional summaries will be provided for AEs that are observed with higher frequency.

Efficacy Analyses:

The primary and secondary efficacy analyses will include all enrolled patients who have received at least one dose of durvalumab, underwent resection and who do not have EGFR mutant tumors (*efficacy population*).

Primary Efficacy Endpoint

The effectiveness of sirolimus followed by durvalumab will be assessed by complete pathologic response rate in the *efficacy population*. If the null hypothesis is rejected then this is evidence that the response rate exceeds 10% when sirolimus followed by durvalumab is given before resection. The one-sided 95% confidence interval (CI) for complete pathologic response will be reported. Exact binomial test will be used to compare the estimated complete pathologic response rate to the historical reference.

Secondary Efficacy Endpoints

The complete pathologic response rates for PDL-1 negative and PDL-1 positive patients in the *efficacy population* will be presented separately.

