2.2 Secondary objective(s)

- To evaluate the efficacy of sirolimus in combination with durvalumab as neoadjuvant treatment for Stage I, II, and IIIA NSCLC by Investigator-assessed response rate per RECIST v1.1, disease free survival and overall survival
- To evaluate response to sirolimus in combination with durvalumab in patients with PD-L1-positive vs. PD-L1-negative tumors by complete pathologic response rate
- To evaluate the association between blood mutation burden and response to sirolimus and durvalumab by overall response rate in PD-L1-positive and PD-L1-negative groups based on mutational burden.
- To evaluate impact of neoadjuvant durvalumab and sirolimus on post-surgical recovery by length of hospital stay after surgery

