3. STUDY DESIGN

3.1 Overview of study design

This is a Phase Ib open-label, single-arm study in newly diagnosed stage I-IIIA NSCLC patients, to test sirolimus in combination with durvalumab as neoadjuvant treatment prior to curative-intent surgical resection. The safety and tolerability as well as efficacy of combination sirolimus with durvalumab will be evaluated in this treatment setting. The study is also designed to investigate a number of laboratory correlative studies to define mechanisms of anti-tumor activity of sirolimus + durvalumab and several potential predictive biomarkers, which will help identify patients who are more likely to respond to treatment. Finally, the study will also include DFS and OS as secondary endpoints.

Up to 31 patients with NSCLC will be enrolled in this study at Emory University Winship Cancer Institute and affiliated sites. Enrollment will occur in 2 parts based on Simon 2 stage design, in which at least 2 of the first 16 patients must achieve pathologic complete response in order for the study to enroll 15 additional patients.

Eligible patients will complete 2 cycles of outpatient study treatment prior to proceeding to standard of care surgical resection. In order to allow a reliable assessment of the contribution of sirolimus versus durvalumab to the observed clinical and PD outcome, treatment will start with sirolimus 6mg orally for one loading dose followed by 2mg orally once daily three weeks prior to the start of durvalumab. Durvalumab will be administered at a dose of 1500mg Q 3 weeks starting on C1D1 for up to 2 cycles that are 21 days in length. Pharmacodynamic analysis will be done using PD samples collected at baseline (tissue) and with blood samples on day -7, C1D1 prior to durvalumab, C1D8, C2D1, C2D8 and at the time of surgery (blood and tissue). Additional post surgery blood samples will be collected at 1, 3, and 6 months post-surgery. See **study schedule of assessments** for schedule of Biomarker collection. Patients will proceed to surgery within a 4-week period post 2nd dose of durvalumab but not earlier than one week after the administration of durvalumab i.e. not earlier than C2D8. Additionally, patients will self-administer heavy water (D2O) 50ml orally three times a day from C1D1 through C1D5 followed by 50ml orally twice a day through the day prior to surgery in order to label dividing cells for research tracking purposes.

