11. STATISTICAL METHODS AND SAMPLE SIZE DETERMINATION

11.1 Description of analysis sets

11.1.1 Safety analysis set

All enrolled patients will be evaluable for safety analyses from the time of their first treatment with sirolimus and/or durvalumab.

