11.1.2 Efficacy analysis set

The primary and secondary efficacy analyses will include all enrolled patients who have received at least one dose of durvalumab, underwent resection and who do not have EGFR mutant tumors (efficacy population).

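### As written, OS is analyzed only in resected patients, so deaths before surgery drop out, and no listed endpoint counts progression before surgery as an event

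*Combined protocol and SAP*

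**What the plan says.** Section 2.2 sets a secondary efficacy objective assessed by "Investigator-assessed response rate per RECIST v1.1, disease free survival and overall survival". Section 3.1 adds that "the study will also include DFS and OS as secondary endpoints", and the synopsis lists both under its efficacy assessments.

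Section 11.1.2 then fixes the population: "The primary and secondary efficacy analyses will include all enrolled patients who have received at least one dose of durvalumab, underwent resection". It also requires a tumor without EGFR mutation. The synopsis gives the same rule ("underwent resection and who do not have EGFR mutant tumors").

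The safety set is wider: "All enrolled patients will be evaluable for safety analyses from the time of their first treatment with sirolimus and/or durvalumab" (Section 11.1.1).

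Section 4.3 states that "All patients will be followed for survival until the end of the study". Later in that section a tracing instruction begins "In order to support key end points of PFS and OS analyses, the survival status of all patients" and continues "in the full analysis and the safety analysis sets should be re-checked". It covers patients lost to follow-up and, through public death registries, those who withdrew consent.

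Section 11.2.2 describes the pCR test, the PD-L1 comparisons for pCR and RECIST response, logistic models and the mutation-burden correlation. It says nothing on how DFS or OS is estimated, from what date, or with what censoring.

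**The concern.** In a neoadjuvant trial, the patient who never reaches the operating room is one of the outcomes of interest. Section 1.6.2 names delayed or prevented surgery as a risk of this design, and Section 4.3 makes progression a reason to stop treatment. An OS estimate limited to resected patients conditions on having come through that period. If it is timed from first dose, everyone analyzed is guaranteed to have survived to surgery, at about weeks 8-9 in the schedule of assessments. If it is timed from surgery, the early deaths are still absent.

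The estimate would then describe patients who were successfully operated on, while a reader would take it as survival under the regimen. Progression before surgery has no home either. DFS is undefined, and PFS appears in no objective or endpoint list; Section 4.3 alone names it as an endpoint.

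**Working it through.** **1. Which set governs OS.**

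- OS is a secondary efficacy endpoint (Sections 2.2 and 3.1, synopsis).
- Section 11.1.2 covers all secondary efficacy analyses and names no exception.
- Section 11.2.2 contains no OS or DFS analysis that assigns another set.
- So the resected, durvalumab-treated, non-EGFR-mutant set governs OS.

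**2. Who is followed but not analyzed.**

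- Patients who die, progress or become inoperable and so are not resected.
- Patients who take sirolimus but never receive durvalumab.
- Patients with EGFR-mutant tumors, resected or not.

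All of these are followed for survival under Section 4.3, so the loss is at analysis and not at collection. Section 9.1.2 even counts a patient with objective progression before the end of cycle 1 as evaluable for response; Section 11.1.2 removes that patient if no resection follows.

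**3. The plan's own figure.** The only design figure is for pCR: 10% versus 25%, at least 2 of 16 to continue, at least 6 of 31 to succeed, one-sided alpha 0.1, power 80%. The exact probability that X1 ≥ 2 of 16 and X1 + X2 ≥ 6 of 31 is 0.0788 at 10% and 0.8053 at 25%. The stated design reproduces and is not in dispute. The plan gives no event count, survival rate, non-resection rate or power for OS or DFS.

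**4. Illustrative size (assumed rates).** Let k of 31 treated patients be unresected, with 2-year OS of S_r if resected and S_u if not. For simplicity, resection is the only exclusion modeled.

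OS in all treated = [(31 − k)·S_r + k·S_u] / 31

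Overstatement = S_r − OS in all treated = (k/31)·(S_r − S_u)

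Take S_r from 80% to 90% and S_u from 0% to 50%. The smallest gap is 80 − 50 = 30 points and the largest is 90 − 0 = 90 points.

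| k | Smallest | Largest |
|---|---|---|
| 2 | (2/31) × 30 = 1.9 points | (2/31) × 90 = 5.8 points |
| 3 | (3/31) × 30 = 2.9 points | (3/31) × 90 = 8.7 points |
| 6 | (6/31) × 30 = 5.8 points | (6/31) × 90 = 17.4 points |

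**5. The same in whole patients (assumed counts).** Suppose 3 of 31 die before surgery and 4 of the 28 resected die later. The efficacy set gives 24/28 = 85.7%; all treated gives 24/31 = 77.4%, a gap of 8.3 points. If instead the 3 unresected patients all survive, all treated gives 27/31 = 87.1%, and the efficacy set is 1.4 points too low. So the direction depends on unresected patients faring worse, which is plausible but not established in the documents.

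**The case against.** The strongest reply has five parts.

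- **Section 4.3 is not a rival analysis plan.** A reader might infer that it demands PFS and OS in all patients and so contradicts Section 11.1.2 outright. It does not: it asks for survival status to be re-checked, which is a data-collection instruction. Collecting more than one set uses is no contradiction. What stands is that it names an endpoint (PFS) found in no objective and a full analysis set that Section 11.1 never defines.
- **DFS in resected patients is defensible.** A reader might extend the charge to DFS. If DFS is timed from resection, only resected patients can contribute. The fault there is the missing time origin, not the restriction.
- **Failure to reach surgery would not be invisible.** Section 11.2 summarizes discontinuations with reasons, the safety set keeps all treated patients, and Section 10.4.9 requires deaths during treatment and follow-up to be reported. This is correct, but none of it enters the survival estimate.
- **The bias may be small.** Section 1.6.2 says PD-1 pathway agents have not significantly precluded surgery in ongoing single-agent studies. Patients must be ECOG 0-1 with life expectancy of at least 26 weeks. Six unresected of 31 (19%) may therefore be high. Sampling error is also large: at 80% with n = 31, the 95% half-width is 1.96 × √(0.8 × 0.2/31) = 14 points. That exceeds most of the range above, but imprecision does not excuse an avoidable bias.
- **Nothing decisive rests on OS.** The go/no-go decision uses pCR, and OS is an unpowered secondary endpoint in a single-arm study. This limits the weight of the point but does not remove it.

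**Conclusion.** The point holds for OS and for progression before surgery. The set definition is a stated rule, and followed literally it drops from OS every patient who fails to reach resection, plus those without durvalumab and those with EGFR-mutant tumors, although their survival is followed. If unresected patients do worse, the reported OS favors the regimen.

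The size cannot be computed from the documents. Under the assumed rates (2-year OS of 80-90% if resected, 0-50% if not), the overstatement is about 2-6 points with 2 unresected of 31 and about 6-17 points with 6. The documents do not support a claim that Section 4.3 prescribes an all-patient survival analysis, that restricting DFS to resected patients is wrong in itself, or that any particular bias is known. The pCR design and its decision rule are unaffected by this point. The change should be made, but it concerns secondary, descriptive results.

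**What to change.** 1. **Sections 11.1.2 and 11.2.2, OS.** Estimate OS by Kaplan-Meier from the first sirolimus dose in all treated patients (the safety set), with a stated censoring rule. Report the current efficacy set as supportive. Patients replaced under Section 4.4 after taking sirolimus stay in the all-treated set for as long as their status is known.
2. **Event-free survival.** Add it in the same set from the same origin, counting progression before surgery, recurrence or death. Use investigator-documented progression where an unresected patient has no scheduled imaging, and state in advance how inoperability without progression is handled.
3. **DFS.** Keep it in resected patients, explicitly timed from surgery, with events and censoring defined.
4. **Section 4.3.** Reconcile PFS and the undefined full analysis set with Sections 2.2 and 11.1.

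The cost is mainly wording. Survival is already followed in everyone. Progression data will be less regular in unresected patients, because the follow-up schedule is anchored to surgery and later imaging is per standard of care (Section 8.1.3, Appendix 2). The estimates will probably be slightly less favorable.

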4.4 Replacement of patients

Patients who withdraw consent prior to administration of durvalumab will be replaced. Patients who discontinue study treatment prematurely will not be replaced.

5. INVESTIGATIONAL PRODUCT(S)

5.1 Durvalumab

5.1.1 Formulation/packaging/storage

Durvalumab will be supplied by AstraZeneca as a 500-mg vial solution for infusion after dilution. The solution contains 50 mg/mL durvalumab, 26 mM histidine/histidine-hydrochloride, 275 mM trehalose dihydrate, and 0.02% weight/volume (w/v) polysorbate 80; it has a pH of 6.0 and density of 1.054 g/mL. The nominal fill volume is 10.0 mL. Investigational product vials are stored at 2°C to 8°C (36°F to 46°F) and must not be frozen. Drug product Investigational Product should be kept in original packaging until use to prevent prolonged light exposure.

5.1.2 Durvalumab doses and treatment regimens

Regimen Description					
Agent	Premedications Precautions	Dose	Route	Schedule	Cycle Length
Durvalumab	None required	1500 mg in NS or D5W	IV over 1 hr	Once every 3 weeks, starting on day 22	21 days (3 weeks)

5.1.3 Study drug preparation

Patients will receive 1500 mg durvalumab via IV infusion q3w for a maximum of 2 doses. Weight based dosing (20 mg/kg) will be utilized for any patient whose body weight drops below to 30 kg or below (≤ 30 kg) while on study.

Preparation of durvalumab doses for administration with an IV bag

The dose of durvalumab (MEDI4736) for administration must be prepared by the Investigator's or site's designated IP manager using aseptic technique. Total time from needle puncture of the durvalumab (MEDI4736) vial to the start of administration should not exceed:

- 24 hours at 2°C to 8°C (36°F to 46°F)
- 4 hours at room temperature

A dose of 1500 mg (for patients > 30 kg in weight) will be administered using an IV bag containing 0.9% (w/v) saline or 5% (w/v) dextrose, with a final durvalumab concentration ranging from 1 to 15 mg/mL, and delivered through an IV administration set with a 0.2- or 0.22- μ m filter. Add

30.0 mL of durvalumab (i.e., 1500 mg of durvalumab) to the IV bag. The IV bag size should be selected such that the final concentration is within 1 to 15 mg/mL. Mix the bag by gently inverting to ensure homogeneity of the dose in the bag.

If weight falls to \leq 30 kg weight-based dosing at 20 mg/kg will be administered using an IV bag containing 0.9% (w/v) saline or 5% (w/v) dextrose, with a final durvalumab concentration ranging from 1 to 15mg/mL and delivered through an IV administration set with a 0.2- or 0.22- μ m filter.

Standard infusion time is 1 hour. In the event that there are interruptions during infusion, the total allowed infusion time should not exceed 8 hours at room temperature.

Do not co-administer other drugs through the same infusion line.

The IV line will be flushed with a volume of IV diluent equal to the priming volume of the infusion set used after the contents of the IV bag are fully administered or complete the infusion according to institutional policy to ensure the full dose is administered. If either preparation time or infusion time exceeds the time limits a new dose must be prepared from new vials. Durvalumab does not contain preservatives, and any unused portion must be discarded.

5.1.4 Monitoring of dose administration

Patients will be monitored before, during and after the infusion with assessment of vital signs at the times specified in the Schedule of Assessment. Patients are monitored (pulse rate, blood pressure) every 30 minutes during the infusion period (including times where infusion rate is slowed or temporarily stopped).

In the event of a \leq Grade 2 infusion-related reaction, the infusion rate of study drug may be decreased by 50% or interrupted until resolution of the event (up to 4 hours) and re-initiated at 50% of the initial rate until completion of the infusion. For patients with a \leq Grade 2 infusion-related reaction, subsequent infusions may be administered at 50% of the initial rate. Acetaminophen and/or an antihistamine (e.g., diphenhydramine) or equivalent medications per institutional standard may be administered at the discretion of the investigator. If the infusion-related reaction is Grade 3 or higher in severity, study drug will be discontinued. The standard infusion time is one hour, however if there are interruptions during infusion, the total allowed time from infusion start to completion of infusion should not exceed 8 hours at room temperature (otherwise requires new infusion preparation). For management of patients who experience an infusion reaction, please refer to the toxicity and management guidelines in **Error! Reference source not found.**

As with any antibody, allergic reactions to dose administration are possible. Appropriate drugs and medical equipment to treat acute anaphylactic reactions must be immediately available, and study personnel must be trained to recognize and treat anaphylaxis. The study site must have immediate access to emergency resuscitation teams and equipment in addition to the ability to admit patients to an intensive care unit if necessary.

